### **7.3 Variables**

We will explore demographic information, past medical history, clinical procedures, medications, encounters (ambulatory, ED, and hospital), and administrative claims (inclusive of costs of care) among the HF population. Examples of variables of interest include age, sex, BMI, comorbid conditions, medication use, healthcare utilization, and costs of care.

### **7.4 Data Sources**

A data broker in Geisinger’s Phenomic Data Analytics and Clinical Data Core (PACDC) will extract EHR data, Geisinger Health Plan (GHP) medical and prescription claims, and patient reported data necessary for the study. Approved study personnel may need to consult individual patient medical records for manual chart review and abstraction if further investigation/validation of the data is needed.

Protected Health Information (PHI) will be limited to medical record numbers (MRNs), dates, GHP insurance numbers, and department and clinician IDs. Approved study personnel conducting the manual chart reviews will be exposed to other elements of PHI, but these elements will not be collected as part of chart abstraction. In addition to PHI, we will also collect data including but not limited to the following:

- Demographics (e.g., age, sex)
- Vitals (e.g., body mass index, blood pressure)
- Encounter and Problem list diagnosis
- Patient-reported data
- Health behaviors (e.g., smoking status)
- Medications (ordered and dispensed)
- Procedures (e.g., surgery)
- Laboratory values
- Utilization of health services (e.g., inpatient, outpatient, emergency room)
- Cost of care
- Social determinants of health data (when available)

### **7.5 Data Management**

Members of the Geisinger approved study team will coordinate with the data broker to pull the necessary data for the study. Members of the Geisinger approved study team who have been trained in chart abstraction will conduct chart reviews as needed. Study data will only be directly accessible to Geisinger approved study team members and stored on password protected computers and/or locked in filing cabinets. Any data shared externally will be de-identified and/or aggregated.

### **7.6 Record Retention**

Records of data generated during the study may be retained indefinitely.

## **8. PROTECTION OF HUMAN SUBJECTS**

Anticipated risk to participants will be minimal. This study will not affect patient care or access to care. While PHI will be requested, it will only be available to approved study team members to limit the risk of breaching confidentiality. All electronic study data will be kept in password-protected locations and any hard copy data will be locked in filing cabinets and only accessible to approved study team members on an as needed basis. Only group-level information without personal identifiers will be included when presenting results or submitting manuscripts for publication. We intend to permanently and securely archive a fully deidentified dataset at a research repository such as Open Science Framework (OSF) in order to be consistent with the best practices for open and reproducible science.

### **8.1 Patient Information**

All parties will comply with all applicable laws, including laws regarding the implementation of organizational and technical measures to ensure protection of patient personal data. Such measures will include omitting patient names or other directly identifiable data in any reports, publications, or other disclosures, except where required by applicable laws.

The personal data will be stored at the study site in electronic and/or paper form and will be password-protected and/or secured in a locked filing cabinet to ensure that only authorized study staff have access. The study site will implement appropriate technical and organizational measures to ensure that the personal data can be recovered in the event of disaster. In the event of a potential personal data breach, the study site shall be responsible for determining whether a personal data breach has in fact occurred and, if so, providing breach notifications as required by law.

## **9. PLANS FOR DISSEMINATING STUDY RESULTS**

We plan to disseminate our findings as abstracts and presentations at national meeting(s) and in peer-reviewed journal(s).

## **10. PROJECT STATUS**

Early education was launched on 8/1/2023 and data collection is ongoing. CDS and MTDM arms launched on 10/9/2023. Outcome data have not yet been extracted or examined as a function of study arms, except in a very limited way for the initial BPA investigation described below.

We removed non-telemedicine telephonic encounters as an inclusion criterion partway into data collection (as of 11/4/2023), based on immediate post-launch investigations of BPAs that were intended to help ensure BPAs were functioning correctly and firing appropriately in terms of patients, clinicians, and encounters. These investigations included chart reviews to examine acknowledgement reasons and prescribing patterns in the referral and order set arms. The results suggested that telephonic encounters were inappropriate occasions in which to expect clinicians to make prescription adjustments, given other pressing reasons for a majority of these calls (e.g., review of lab results, scheduling appointments) and very low rates of prescribing during these encounters. Prescribing rates were not compared between the no-BPA control arm and the CDS arms, and no other outcomes were examined.

Telemedicine telephonic encounters remain a valid inclusion criterion, as those are scheduled appointments appropriate for prescribing.

Within the referral arm only, data on referral rates across clinicians were monitored and chart reviews conducted to better understand where and why referrals to MTDM were not occurring for certain clinicians. These data were used to inform follow-up by MTDM pharmacists and potential escalation by clinical leadership to overcome lack of awareness and educate clinicians on the purpose and appropriate use of the referral. For example, if referral rate to MTDM for a given clinician was below 50% in February 2024, the study PI contacted the clinicians to educate or remind them about the benefits of pharmacy co-management.

Delayed education sessions began in early August 2024. This was anticipated to occur after final data were collected, but enrollment was still incomplete at the time. We will limit our primary education analysis so it only includes encounters before the delayed education sessions began (i.e. the period where the delayed education group had not yet experienced education), so the delayed education encounters can be used as controls. However, follow-up exploratory analyses will include encounters after delayed education so we can examine main effects of delayed education, or interactions between delayed education and ongoing CDS interventions.

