The target audience for this education program are Cardiology clinicians (physicians (MD, DO) and advanced practitioners (PA, CRNP)) at Geisinger. Three clinics were selected for early education (i.e. before additional CDS and pharmacist referral interventions) and two clinics were reserved for late education (timed to occur after sufficient time has elapsed to assess the impact of the early education on its own). The early education programs were delivered over one month to each clinic with in-person attendance being encouraged.

Topics delivered in the early education sessions included:

1. Sacubitril / Valsartan (ARNI) in CHF
2. SGLT2 inhibitors in CHF
  - a. SGLT2i in Cardiovascular Disease & HFrEF
  - b. SGLT2i in HFrEF with Diabetes: What the Cardiologist should know
3. Management of HFrEF and chronic kidney disease (CKD)
4. Geisinger Pharmacist role in HFrEF

The early education sessions were delivered live, at each clinic location separately on a given date (either in-person or virtually depending on clinic preference).

Participants were encouraged by the lead PI to attend the live sessions if they were being offered at their clinic location. Continuing medical education (CME) credits were provided to attendees where applicable and lunch was provided during the live sessions. Presentations lasted about 30 minutes with a question-and-answer session to follow. An RSVP request was asked of those attending. Those missing their sessions were invited to a virtual session being held to try to increase attendance rates. The virtual sessions were recorded. The same approach will be used for delayed education.

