**Other pre-specified effectiveness outcomes:**

- All-cause mortality or emergency visit or hospitalization for heart failure, within 365 days of index visit. This will be assessed as patient death (yes/no), patient with emergency visit with a primary diagnosis of heart failure (yes/no), or admission for inpatient hospitalization with primary diagnosis of heart failure (yes/no).
- Optimal GDMT dosing (at least 50% of target dose) on all classes (with or without ARNI), within 180 days of index visit.
- Increased dosing or initiation for each individual class, within 180 days of index visit.
- Decreased dosing or removal for each individual class, within 180 days of index visit.
- Timing of increases in GDMT over 180 days since index visit.
- Economic outcomes such as (1) return on investment (ROI) and (2) cost effectiveness (CE) of CDS and MTDM interventions compared with standard of care (using modeling approaches specified in the ROI and CE analysis section above).

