#### 7.2.2 Approach for comparisons across intervention arms

*CDS analyses:* We will test whether each outcome differs as a function of each CDS active arm (CDS-OS and CDS-MTDM) relative to no-CDS control. Regressions will include as covariates education arm and interactions between CDS and education. We will retain both terms if the interaction is significant and retain the main effect if only it is significant. The education variable in CDS analyses will be coded as delayed education (baseline), early education, other (for clinicians who were not in the system early enough to be included in an education arm, to avoid either diluting or biasing the education effects).

As an exploratory analysis, we will compare CDS-MTDM against CDS-OS to see which is most effective.

Additionally, covariates will be added to exploratory versions of the final models as sensitivity analyses, to adjust for measured differences across clinicians, such as role, number of patients seen, and baseline rates of prescribing each of the GDMT classes. We have no *a priori* hypotheses about the moderating effects of these covariates.

*Education analyses:* We will test whether each outcome differs as a function of early education relative to delayed education. Regressions will include as covariates CDS arm and interactions between CDS and education. We will retain both terms if the interaction is significant and retain the main effect if only it is significant. Assignment to early versus delayed education is not random; therefore, regression analysis comparing education to no-education controls will adjust for as many relevant covariates as possible, including baseline prescribing rates.

In these analyses, we will exclude clinicians who were not present throughout the data collection period, beginning at assignment to early education. That is, we only intend to include clinicians in early and delayed education arms who theoretically could have been exposed to the education and who then had time to treat patients based on what they learned.

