### 7.2.3 Regression Specifications

For all outcomes except timing of GDMT increases and ROI outcomes, ordinary least squares (OLS) regressions will be run with heteroskedasticity-robust standard errors clustered at the clinician level (to account for clustering of patients within clinicians). We will also explore the effect of clustering standard errors at the clinic level.

We will run a survival analysis to assess timing of GDMT increases.

Cost and outcomes estimate for the cost-effectiveness model will be obtained using EHR data, claims data, and literature-based sources. These data will be used to develop a decision tree analytical model with a state transition Markov cohort simulation to compute incremental cost effectiveness ratios (ICER), cost-effectiveness acceptance curves will be generated for all cost-effectiveness measurements. The effects of uncertainties from the model parameters will be evaluated by deterministic and stochastic sensitivity analyses. Following the World Health Organization's guidelines, we will define the willingness-to-pay (WTP) threshold as 1 to 3 times the local gross domestic product per capita. Interventions with an ICER below the threshold will be considered cost-effective. We will also compare the total dollar amount spent on implementing this program against the cost savings, if any, attributable to the interventions (CDS-OS + CDS-MTDM) to calculate the corresponding ROI.

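### The education analysis is cut off by encounter date, not by the end of the outcome window, so some delayed-site follow-up comes after those sites' own education: negligible to small at 30 days, potentially material at 180 and 365

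*Combined protocol and SAP*

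**What the plan says.** Five practice sites were assigned to early or delayed education (section 6.1), three early and two late (section 6.7, Focused Education). Section 6.7 describes the late sessions as "timed to occur after sufficient time has elapsed to assess the impact of the early education on its own".

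Section 10 dates the early education launch to 8/1/2023, the CDS and pharmacist arms to 10/9/2023, and the delayed sessions to early August 2024. Of the delayed sessions it says: "This was anticipated to occur after final data were collected, but enrollment was still incomplete at the time". The response is: "We will limit our primary education analysis so it only includes encounters before the delayed education sessions began". The stated purpose is that delayed-site encounters can then act as controls. Later encounters go to exploratory analyses.

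The outcomes to which this applies are set out elsewhere:

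- Section 7.2.2: "We will test whether each outcome differs as a function of early education relative to delayed education". It adds: "Assignment to early versus delayed education is not random".
- Section 6.8: the primary outcome runs 30 days from the index visit and the secondary outcomes run to 90 days. The other pre-specified outcomes run to 180 days (for example "Timing of increases in GDMT over 180 days since index visit") or a year ("All-cause mortality or emergency visit or hospitalization for heart failure, within 365 days of index visit").
- Section 7.2.3: "We will run a survival analysis to assess timing of GDMT increases". No censoring rule is given.

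**The concern.** The cut-off selects on when the visit took place, but the outcome is what happens afterwards. A delayed-site encounter on 31 July 2024 is kept as a not-yet-educated control, although nearly all of its window follows the start of the delayed sessions. No section requires the window to end before those sessions, censors follow-up at that date, or limits the education contrast to the short outcomes. The rule was written to repair an overlap caused by slow enrolment, and it repairs it only in part.

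If education raises prescribing, control follow-up that continues into the educated period brings the two groups closer together. The risk is that a null early-versus-delayed result at 180 days is read as no effect of education, or that the 365-day result is labelled as educated versus not yet educated when that label does not fit.

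**Working it through.** **The plan's own figure.** The only number given for the education contrast is 80% power for about 5.5 percentage points (section 7.1). It came from a simulation, and the documents give no baseline rate, intraclass correlation (ICC) or cluster sizes, so it cannot be reproduced. The plan gives no figure for follow-up overlap.

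**Inputs.**
- First delayed session: assumed 1 August 2024 (section 10 says only early August).
- Start of retained encounters: 1 August 2023, giving T = 366 days, or 9 October 2023, giving T = 297 days (both dates from section 10). The earlier start is better supported. Section 6.7 has silent alerts recording eligible encounters in the two months before CDS launch, and section 7.2.2 counts clinicians from assignment to early education.
- Window length w: 30, 60, 90, 180 or 365 days (section 6.8).
- Accrual pattern: not given. Uniform accrual is the base case, with front-loaded accrual as a sensitivity.

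**Formulas, uniform accrual.** Share of retained windows that cross the date = min(w, T)/T. Mean share of window time after the date = w/(2T) if w ≤ T, otherwise 1 − T/(2w).

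For w = 180: 180/366 = 49.2% and 180/297 = 60.6% cross; 180/732 = 24.6% and 180/594 = 30.3% of window time falls after the date. For w = 365: 365/366 = 99.7% and 100% cross; 365/732 = 49.9% and 1 − 297/730 = 59.3% of window time falls after it.

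| Window | Crossing, T=366 | Crossing, T=297 | Time after, T=366 | Time after, T=297 |
|---|---|---|---|---|
| 30 d | 8.2% | 10.1% | 4.1% | 5.1% |
| 60 d | 16.4% | 20.2% | 8.2% | 10.1% |
| 90 d | 24.6% | 30.3% | 12.3% | 15.2% |
| 180 d | 49.2% | 60.6% | 24.6% | 30.3% |
| 365 d | 99.7% | 100% | 49.9% | 59.3% |

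**Front-loaded accrual.** Two assumed shapes were used: accrual falling exponentially with a half-life of 90 or 180 days, and cumulative accrual proportional to the square root of time. Over both values of T, crossing is 2-6% (30 d), 4-12% (60 d), 6-19% (90 d), 19-47% (180 d) and 95-100% (365 d). Time after the date is 1-3%, 2-6%, 3-9%, 7-21% and 29-52%. As an example, the square-root shape at 180 days with T = 366 gives 1 − √(186/366) = 28.7% crossing.

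**Delay before education acts.** Section 6.7 says early education took a month per clinic and that the delayed programme follows the same approach. If delayed education acts only 30 days after the first session, the uniform time shares become (w − 30)²/(2wT) when w − 30 ≤ T: 0% at 30 days and 150²/(2 × 180 × T) = 17-21% at 180. At 365 days the share is 42-51%.

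**What this could do to an estimate.** Suppose a true 5.5-point effect, prescribing changes spread evenly over the window, and delayed education acting at once and in full. The loss is then 5.5 × 4.1-5.1% = 0.23-0.28 points at 30 days and 5.5 × 24.6-30.3% = 1.35-1.67 points at 180. These are upper-end figures under uniform accrual. Section 7.1 does not tie the 5.5 points to 180 days, so that use is only an illustration.

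**The case against.** **Little is at stake.** The contrast is secondary and non-randomised, the 30-day effect is small, and the 180- and 365-day outcomes sit in the lowest effectiveness tier with no power claimed for them. Section 7.2.2 already words the contrast as early relative to delayed education. This stands, and it sets the severity. It does not remove the gap, because section 10 justifies its cut-off by the delayed group's uneducated status, and section 7.2.2 also speaks of no-education controls.

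**Prescribing may cluster at the index visit.** If so, most outcomes precede any delayed session and the time shares overstate the dilution. That stands too, and is strongest at 30 days. It is weaker for the 180-day dosing and timing outcomes, which are about later titration.

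**The primary education analysis might mean the 30-day outcome only.** Section 10 contrasts it with exploratory analyses that add later encounters, not with longer outcomes, so the broad reading is better supported. Under the narrow one, the longer windows have no stated cut-off.

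Some further inferences are tempting but not supported:

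- *The timing in section 6.7 was breached.* It asks only that enough time pass, and about a year did.
- *The Table 1 visit schedule shows how many second visits fall after the date, or that dilution is nil up to 90 days.* Table 1 covers pharmacist co-management, in an arm with 10% of clinicians. No visit interval is given for the rest.
- *Closing the windows necessarily costs, or gains, power.* Take the 180-day illustration above, with the standard error anchored on section 7.1. Power under the section 10 rule is 50-56%. With windows closed it is 42-52% if standard errors scale as 1/√n, but 52-70% with an illustrative ICC of 0.015-0.06 and about 42 patients per clinician. The sign depends on an ICC that the documents do not give. Nor do they show that the section 7.1 figure allows for the encounters and clinicians already excluded.
- *The randomised CDS contrasts are untouched, or are biased.* Neither is shown. Their models carry education terms with delayed education as baseline, and the encounter cut-off is stated only for the education analysis.

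**Conclusion.** The concern holds as a minor point about the education contrast. It is certain from the text that the cut-off is by encounter date and that no window is closed or censored at the first delayed session. The size is uncertain, because accrual, the exact August date and the timing of prescribing within the window are not given. On the stated assumptions the overlap is negligible to small at 30 days, intermediate at 60 and 90, and potentially material at 180 and 365. Its direction is toward no difference if education works.

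A reader might infer that the education analysis as a whole is invalid. The documents do not support that: the section 10 rule removes most of the problem at 30 days, and the crossing shares measure opportunity for exposure, not observed bias. At 365 days almost every retained window crosses the date, so an educated versus not-yet-educated label cannot be sustained there. Even so, education would have to work through later prescribing to alter the composite.

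**What to change.** 1. **180-day timing of increase.** Censor the education analysis at the first delayed session, in early and delayed sites alike.
2. **30-, 60-, 90- and 180-day education outcomes.** Keep the section 10 rule and add a prespecified sensitivity analysis limited to encounters, in both groups, whose whole window closes before the first delayed session. If that was 1 August 2024, the last index dates are 1 July, 1 June, 2 May and 2 February 2024. Do not read a null 180-day result as no education effect without it.
3. **365-day composite.** Report it as early versus delayed rollout, not as educated versus not yet educated.

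The cost is a few lines of SAP text, one censoring date and one date filter per outcome. The timing analysis gives up at most 25-30% of its 180-day window time under uniform accrual. The sensitivity analysis drops 8-10% of encounters at 30 days, 16-20% at 60, 25-30% at 90 and 49-61% at 180 under uniform accrual, and fewer if accrual was front-loaded. That loss is why it should be added to the section 10 analysis and not replace it.

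Section 10, in the version dated 4 September 2024, says outcomes had not been examined by arm apart from a limited alert check. The change could be prespecified on that footing if it still holds; later status is not known from the documents.
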